6.7.2. Unsolicited Treatment-emergent Adverse Events

A TEAE is defined as any event that is not present before exposure to the study intervention or any event already present that worsens in intensity or frequency after exposure. Worsening of a pre-existing condition after vaccination will be reported as a new AE.

AEs will also be evaluated by the investigator for the coexistence of MAAEs and/or AESIs. A MAAE is an AE that leads to an unscheduled or scheduled visit to a healthcare practitioner. AESIs for this study are pre-defined in the protocol ([Table 12](#)) including thrombocytopenia, neurologic diseases, anaphylaxis, and myocarditis/pericarditis.

Unsolicited AEs will be collected from Day 1 up to 28 days after vaccination on the AE page and reactogenicity page of the eCRF. SAEs, MAAEs, AESIs, and AEs leading to discontinuation from study participation will be collected from Day 1 until the end of participation in the study. Analyses of unsolicited AEs will be provided for events occurring up to 28 days after vaccination unless otherwise specified.

Unsolicited AEs will be coded by PT and SOC using MedDRA and summarized by vaccination group.

All summary tables for unsolicited AEs will be presented by SOC and PT or by PT only for TEAEs with counts of participants included. SOC will be displayed in internationally agreed order. PTs will be displayed in descending order of frequency in the mRNA-1010 group and

then alphabetically within SOC. When summarizing the number and percentage of participants with an event, participants with multiple occurrences of the same AE or a continuing AE will be counted once. Only the maximum severity level will be presented in the severity summaries, and the strongest relationship level will be presented in the relationship summaries.

Unsolicited TEAEs occurring up to 28 days after IP injection and occurring throughout the study (up to Day 361/EoS) Will be summarized.

In addition, the number of participants with occurrences of selected TEAEs of clinical interest identified by standardized MedDRA queries (SMQ) will be summarized. SMQ will be summarized by PT, if applicable. Detailed descriptions of SMQ are presented in [Table 15](#) and [Table 16](#).

Percentages will be based upon the number of participants in the Safety Set within each treatment group.

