8.9. Safety Assessments

Safety assessments will include monitoring and recording of the following for each participant in the study:

- Solicited local and systemic ARs (Section 8.10.3) that occur through the 7 days following the study intervention (ie, the day of injection and 6 subsequent days). Solicited ARs will be recorded daily using eDiary (Section 8.9.4).
- Unsolicited AEs (Section 8.10.1) observed or reported through the 28 days following the study intervention (ie, the day of injection and 27 subsequent days). Unsolicited AEs are defined in Section 8.10.1.

- AEs leading to discontinuation from study participation from Day 1 through Day 361 (Month 12)/EoS or withdrawal from the study.
- MAAEs from Day 1 through Day 361 (Month 12)/EoS or withdrawal from the study. MAAEs are defined in [Section 8.10.4](#).
- AESIs from Day 1 through Day 361 (Month 12)/EoS or withdrawal from the study. AESIs are defined in [Section 8.10.6](#).
- SAEs from Day 1 through Day 361 (Month 12)/EoS or withdrawal from the study. SAEs are defined in [Section 8.10.2](#).
- Vital signs measurement.
- Details of all pregnancies in female participants will be collected after the start of study intervention and until the end of their participation in the study ([Section 8.9.5](#)). All pregnancies must be followed to determine the outcome; however, pregnancy related-data received after the end of the study may not be collected in the clinical database.

Planned time points for all safety assessments are provided in the SoE ([Table 1](#)).

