8.9.6. Recording and Follow-up of an AE and/or SAE

The Investigator is responsible for ensuring that all AEs and SAEs are recorded in the eCRF and reported to the Sponsor.

Solicited ARs will be collected from Day 1 through 7 days after the study intervention (ie, the day of injection and 6 subsequent days). Other (unsolicited) AEs will be collected from Day 1 through 28 days after the study intervention (ie, the day of injection and 27 subsequent days).

MAAEs, SAEs, and AESIs will be collected from participants as specified in the SoE (Table 1) from Day 1 until the end of their participation in the study.

At every clinic visit or telephone contact, participants will be asked a standard question to elicit any medically related changes in their well-being (including surveillance for respiratory viral infection symptoms) according to the scripts provided. Participants will also be asked if they have been hospitalized, had any accidents, used any new medications, changed concomitant medication regimens (both prescription and over-the-counter medications), or had any non-study vaccinations.

In addition to participant observations, physical examination findings and other documents relevant to participant safety classified as an AE will be documented on the AE page of the eCRF.

After the initial AE/SAE report, the Investigator is required to proactively follow each participant at subsequent visits/contacts. All AEs and SAEs will be treated as medically appropriate and followed until resolution, stabilization, the event is otherwise explained, or the participant is LTFU (as defined in Section 7.2).

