8.9.7. Reporting Adverse Events

The Investigator is responsible for reporting all AEs that are observed or reported during the study, regardless of their relationship to the study intervention or their clinical significance. If there is any doubt as to whether a clinical observation is an AE, the event should be reported.

All unsolicited AEs reported or observed during the study will be recorded on the AE page of the eCRF. Information to be collected includes, type of event, time of onset, Investigator-specified assessment of severity (impact on activities of daily living) and relationship to study intervention, time of resolution of the event, seriousness, as well as any required treatment or evaluations, and outcome. The unsolicited AEs resulting from concurrent illnesses, reactions to concurrent illnesses, reactions to concurrent medications, or progression of disease states must also be reported. All AEs will be followed until they are resolved or stable or judged by the Investigator to be not clinically significant. The Medical Dictionary for Regulatory Activities (MedDRA) will be used to code all unsolicited AEs.

Refer to Section 8.9.9 for reporting of medical occurrences that begin before the start of study intervention administration but after obtaining informed consent.

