6.1.7. Analysis Periods

The following analysis periods and vaccination groups will be used for efficacy analyses:

| Vaccination Group | Description | Analysis Period for Efficacy |
|-------------------------|--|---|
| mRNA-1010 μg | Participants randomized to mRNA-1010 μg | From randomization to the earliest date of study discontinuation, study |

| | | |
|--------------------------------|--|---|
| Fluarix Quadrivalent 0.5 μg | Participants randomized to active comparator (Fluarix quadrivalent 0.5 μg) | completion, death, or data cutoff date for efficacy |
|--------------------------------|--|---|

The analysis period and vaccination groups for Safety analyses are summarized below:

| Vaccination Group | Description | Analysis Period for Safety |
|--------------------------------|---|--|
| mRNA-1010 0.5 μg | Participants received mRNA-1010 0.5 μg | From the day of vaccination (Day 1) to the earliest date of study discontinuation, study completion, death, or data cutoff date for safety |
| Fluarix Quadrivalent 0.5 μg | Participants received active comparator (Fluarix quadrivalent 0.5 μg) | |

The above safety analysis period will be used to summarize unsolicited treatment-emergent adverse events (TEAEs), MAAEs, SAEs, AESIs, and AEs leading to discontinuation throughout the study.

The period up to 7 days after injection, that starts at the day of injection and continues through 6 subsequent days, will be used for analyses of solicited ARs.

The period up to 28 days after injection, that starts at the day of injection and continues through 27 subsequent days, will be used as the primary analysis period for safety analyses including unsolicited AEs, except for solicited ARs.

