6.7.1.3. TEAEs by Preferred Term

A summary table of all unsolicited TEAEs will be provided by PT in descending order of frequency in the mRNA-1010 group.

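### The SAP promises a summary of any unsolicited TEAE to Day 361, but unselected unsolicited AEs are collected only on Days 1 to 28

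*SAP*

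**What the plan says.** Two places in the SAP commit to a whole-study summary of unsolicited TEAEs.

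- SAP 6.7.2: "Unsolicited TEAEs occurring up to 28 days after IP injection and occurring throughout the study (up to Day 361/EoS) Will be summarized".
- SAP 6.1.7, after defining a safety period from Day 1 to discontinuation, completion, death or data cutoff: "The above safety analysis period will be used to summarize unsolicited treatment-emergent adverse events (TEAEs), MAAEs, SAEs, AESIs, and AEs leading to discontinuation".

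The collection rules are narrower.

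- SAP 6.7.2: "Unsolicited AEs will be collected from Day 1 up to 28 days after vaccination". The same paragraph carries SAEs, MAAEs, AESIs and AEs leading to discontinuation to the end of participation.
- Protocol 8.9.6: "Other (unsolicited) AEs will be collected from Day 1 through 28 days after the study intervention". Protocol 8.9 and 8.9.6 both define the window as the injection day plus 27 days.
- The Schedule of Events (Protocol Table 1, SAP Table 6) marks unsolicited AE recording at Days 1, 8 and 29 only. The selected classes are marked at every contact to Day 361.

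One protocol section has no time limit. Protocol 8.9.7: "All unsolicited AEs reported or observed during the study will be recorded on the AE page of the eCRF".

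**The concern.** An incidence table needs one event definition over its whole period. Under the collection rules, any unsolicited AE counts up to Day 28. From Day 29 an AE counts only if it is serious, medically attended, of special interest or a cause of discontinuation. A single percentage for any unsolicited TEAE through Day 361 would mix the two. SAP 6.7.2 takes percentages over the whole Safety Set, so the figure would look like an ordinary incidence. It would understate total AEs and tilt the later part of the period towards medically attended events.

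Protocol 8.9.7 adds a second difficulty. A site that follows it could enter a mild, unattended AE from, say, Day 100. A site that follows 8.9.6 and the Schedule would not. The later part of the figure could then depend partly on which section a site applied.

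**Working it through.** The documents give no event count or rate for this summary, so there is no figure of the plan to reproduce. The check is day arithmetic and a comparison of the texts.

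**Days outside full collection**

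1. Collection window (Protocol 8.9, 8.9.6): 1 + 27 = 28 days, Day 1 to Day 28.
2. Summary period (SAP 6.7.2): Day 1 to Day 361, 361 days.
3. Days with full collection: 28/361 = 7.8%.
4. Days with selective collection: 361 − 28 = 333, and 333/361 = 92.2%.
5. Other conventions: a cut at Day 29 gives 332/361 = 92.0%. Using the visit windows in the Schedule (Day 29 up to +3, Day 361 ± 14), the extremes are (347 − 32)/347 = 315/347 = 90.8% and (375 − 28)/375 = 347/375 = 92.5%.

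This is a share of calendar days. It is not a share of events lost.

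**What is missing after Day 28**

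SAEs, MAAEs, AESIs and AEs leading to discontinuation are collected for the whole study. Protocol 8.10.4 makes the MAAE class broad: any AE leading to an unscheduled visit to a healthcare practitioner, and every RT-PCR-confirmed influenza infection. The gap is therefore events that are non-serious, not medically attended, not of special interest and not a cause of discontinuation. The documents give no basis for counting these.

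**Which tables are touched**

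- The overview (SAP 6.7.1.1), the main SOC and PT tables (6.7.1.2) and the subgroup tables (6.7.1.5) state a 28-day period.
- The whole-study tables listed in 6.7.1.2 cover SAEs, AESIs, MAAEs, AEs leading to discontinuation and AEs leading to death. All of these are collected throughout.
- The PT-only table (6.7.1.3) gives no period: "A summary table of all unsolicited TEAEs will be provided by PT in descending order of frequency in the mRNA-1010 group". The severity tables (6.7.1.4) give none either. SAP 6.7.2 sets 28 days as the default unless something else is specified, and neither section specifies otherwise. They fall under the default.
- The sentences in 6.7.2 and 6.1.7 remain. They name unsolicited TEAEs explicitly, and 6.1.7 lists them beside the selected classes rather than as a label for them.

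**Protocol 8.9.7 against the rest**

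Protocol 8.9, 8.9.6 and the Schedule stop at Day 28. Section 8.9.7 asks for all AEs during the study. The telephone script in 8.9.3 asks about AEs in general as well as the selected classes. Section 8.9.2 points the other way: an ILI assessment visit after Day 29 is captured as an AE only if it meets the MAAE definition or influenza is confirmed by RT-PCR.

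**The case against.** The strongest reply is that the SAP's own table list already does the right thing. No listed table explicitly shows any unsolicited TEAE through Day 361. SAP 6.1.7 also names the 28-day window as the primary period for unsolicited AEs, and 6.7.1.2 uses the word unsolicited as an umbrella for SAEs, AESIs and MAAEs. On that reading the sentence in 6.7.2 merely introduces two sets of tables. This may well be the intent, and it is why the point is minor. It does not remove the problem. The 28-day default yields wherever another period is specified, the sentence in 6.7.2 specifies one, and 6.1.7 repeats it.

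On Protocol 8.9.7, one can say that it describes what is recorded and on which form, not for how long, and that the 28-day limit appears in the endpoint, the Schedule and two other sections. That is reasonable, but 8.9.7 refers to the whole study and does not state the limit.

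A plain exclusion of recorded later AEs from every table could also be criticised for hiding safety data. That is fair, and the fix allows a labelled table.

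**Conclusion.** The concern holds as a minor inconsistency. SAP 6.7.2 and 6.1.7 state an analysis that the data collection cannot support: an any-unsolicited-TEAE summary whose event definition changes at Day 28, with 333 of 361 days (92.2%; 90.8% to 92.5% under other day conventions) under selective collection. This takes the two sentences literally and takes the Schedule as the operative collection rule.

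A reader might infer more than the documents support:

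- **That about 92% of events are missing.** The figure counts days. The four selected classes are collected throughout, and the number of other events is unknown.
- **That site practice does drive the result.** Section 8.9.7 makes uneven recording possible; nothing shows that it occurs.
- **That the comparison between arms is biased.** Allocation is randomised 1:1 and assessment is observer-blind. Uneven recording would mainly affect the level and the mix of terms and severity, and no between-arm bias is shown.
- **That the PT-only and severity tables are affected.** They fall under the 28-day default.

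The primary safety endpoint for unsolicited AEs runs through 28 days and is unaffected. AE summaries are descriptive, and no success criterion depends on the whole-study figure.

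**What to change.** 1. In SAP 6.7.2 and 6.1.7, limit summaries of any unsolicited TEAE to onset on Days 1 to 28.
2. In the same places, limit whole-study summaries to SAEs, MAAEs, AESIs, AEs leading to discontinuation and AEs leading to death, matching the list in SAP 6.7.1.2.
3. Show any other AE recorded after Day 28 in the unsolicited AE listing planned in SAP 6.7.1.1, or in a table clearly labelled as not systematically collected.
4. Optionally, state the 28-day period in SAP 6.7.1.3 and 6.7.1.4.
5. Reconcile Protocol 8.9.7 with 8.9.6 and the Schedule of Events, so that sites have one recording rule after Day 28.

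The cost is a few sentences of SAP text, an onset-date filter in programming and one sentence in the protocol. Nothing further needs to be collected.

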6.7.1.1. Overview of Unsolicited TEAEs

An overall summary of unsolicited TEAEs occurring up to 28 days after IP injection including the number and percentage of participants, along with the number of events, by vaccination group who experience the following will be presented:

- Any unsolicited TEAEs
- Any unsolicited treatment-related TEAEs
- Any serious TEAEs
- Any treatment-related serious TEAEs
- Any unsolicited severe TEAEs
- Any unsolicited treatment-related severe TEAEs
- Any unsolicited treatment-emergent MAAEs
- Any unsolicited treatment-related treatment-emergent MAAEs

- Any unsolicited treatment emergent AESIs
- Any unsolicited TEAEs leading to discontinuation from participation in the study
- Any unsolicited TEAEs that are fatal

In addition, separate listings containing individual participant AE data for unsolicited AEs, unsolicited serious AEs, unsolicited severe AEs, unsolicited MAAEs, unsolicited AESIs as assessed by investigator, unsolicited AEs leading to discontinuation from participation in the study, and unsolicited adverse events leading to death will be produced. A separate listing of deaths will also include the cause of death.

6.7.1.2. TEAEs by System Organ Class and Preferred Term

The following summary tables of TEAEs occurring up to 28 days after IP injection will be provided by SOC and PT using frequency counts and percentages (i.e., number and percentage of participants with an event) and number of events:

- Any unsolicited TEAEs
- Any unsolicited treatment-related TEAEs
- Any serious TEAEs
- Any treatment-related serious TEAEs
- Any unsolicited severe TEAEs
- Any unsolicited treatment-related severe TEAEs
- Any unsolicited treatment-emergent MAAEs
- Any unsolicited treatment-related treatment-emergent MAAEs
- Any unsolicited treatment emergent AESIs
- Any unsolicited TEAEs leading to discontinuation from participation in the study.

Unsolicited TEAEs and unsolicited treatment-related TEAEs will be summarized by SOC and PT for TEAEs with occurrence in $\geq 1\%$ of participants in any vaccination group based

on PT and presented by SOC and PT and maximum severity using frequency counts and percentages.

Summary tables for all unsolicited SAEs, AESIs, MAAEs, AEs leading to discontinuation from the study, and AEs leading to death occurring throughout the study (up to Day 361 (Month 12)/EoS) will be provided by SOC and PT as applicable.

6.7.1.3. TEAEs by Preferred Term

A summary table of all unsolicited TEAEs will be provided by PT in descending order of frequency in the mRNA-1010 group.

6.7.1.4. TEAEs by Severity

The following summary tables of TEAEs will be provided by the maximum severity grade using frequency counts and percentages:

- All unsolicited TEAEs
- All unsolicited treatment-related TEAEs

6.7.1.5. Subgroup Analysis of TEAEs

An overall summary of unsolicited TEAEs occurring up to 28 days after IP injection will be conducted for each of the following subgroups ([Table 2](#)) based on [Section 6.7.2.1](#).

- Age group 1: ≥ 50 to < 65 years or ≥ 65 years
- Age group 2: ≥ 50 to < 65 years, ≥ 65 to < 75 years, or ≥ 75 years
- Sex: Female or Male
- Race: White, Black or African American, Asian, or Other

Summary tables for unsolicited TEAEs, treatment-related TEAEs, and SAEs occurring up to 28 days after IP injection will be presented by SOC and PT for each subgroup.

6.7.1.6. Death

The total number of deaths due to any cause and time of death from the injection (numeric and by time point window) will be summarized.

6.7.3. Other Safety Data

6.7.1.1. Vital Sign Measurements

On Day 1, vital sign measurements will be collected once prior to vaccination and approximately 30 minutes after vaccination (prior to discharge of the participant). Vital signs may be collected at other clinic visits in conjunction with a symptom-directed physical examination.

Vital sign measurements will include the following:

- Systolic and diastolic blood pressures
- Heart rate
- Respiratory rate
- Body temperature

The vital sign measurements will be presented in a data listing. The toxicity grade will also be included in the data listing.

Vital signs meeting the toxicity grading criteria for Grade 3 or higher as presented in [Appendix H](#) will be listed separately.

Observed values and changes from pre-injection (baseline) to post-injection at Day 1 for all vital sign measurements will be summarized by vaccination group.

Shift from pre-injection to post-injection results in vital sign toxicity grades at Day 1 will also be summarized by vaccination group.

6.7.1.2. Pregnancy Test

Pregnancy test results will be presented in a listing.

6.7.4. COVID impact

A listing will be provided for the impact of COVID-19 on the execution of the study.

6.8. Data Safety Monitoring Board

A DSMB will be used throughout the conduct of this study. This committee will be composed of independent members with relevant therapeutic and/or biostatistical expertise

to allow for the ongoing review of safety data from this study population. Safety data will be reviewed according to intervals defined in the DSMB charter and will also occur as needed.

The DSMB will review the IA results and make recommendations to the Sponsor in terms of study results reporting and unblinding based on the boundaries of early efficacy as described in this SAP.

The Sponsor may also request that the DSMB conduct ad hoc reviews of safety events from this study. The DSMB composition, its remit, and frequency of data review will be further defined in the DSMB charter.

7. Changes from Planned Analyses in Protocol

No changes have been made to those analyses planned in the protocol.

8. References

Department of Health and Human Services (DHHS), Food and Drug Administration (FDA), Center for Biologics Evaluation and Research (US). Guidance for industry: Toxicity grading scale for healthy adult and adolescent volunteers enrolled in preventative vaccine clinical trials. September 2007.

Available from:

<https://www.fda.gov/downloads/BiologicsBloodVaccines/GuidanceComplianceRegulatoryInformation/Guidances/Vaccines/ucm091977.pdf>.

9. List of Appendices

9.1. Appendix A Schedule of Events

Table 6: Schedule of Events

| Visit Number | | 1 | 2 | 3 | 4 | 5 | 6 | 7 | USV |
|--|------------------------|---------------|----|--------------------|-----|------|------|----------|-----------|
| Type of Visit/Contact | C | C | SC | C ¹ /SC | SC | SC | SC | SC | C |
| Month Timepoint | | | | M1 | M3 | M6 | M9 | M12 | Up to M12 |
| Study Visit | Screening ² | D1 (Baseline) | D8 | D29 | D91 | D181 | D271 | D361/EoS | USV |
| Window Allowance (Days) | -28 | N/A | ±2 | -7 to +3 | ±5 | ±14 | ±14 | ±14 | N/A |
| Informed consent form, demographics, vaccination and, medical history ³ | X | | | | | | | | |
| Inclusion/exclusion criteria | X | X | | | | | | | |
| Physical examination ⁴ | X | | | | | | | | |
| Vital signs ⁵ | X | X | | | | | | | |
| Pregnancy testing ⁶ | X | X | | | | | | | |
| Randomization | | X | | | | | | | |
| Blood collection for immune response biomarkers subset and/or transcriptomics (optional) subset ⁷ | | X | | X | | | | | |
| Blood collection for future research sample (optional) ⁸ | | X | | | | | | | |
| Study vaccination (including 30-minute post-dosing observation period) ⁹ | | X | | | | | | | |
| Collection of EFS ¹⁰ | | X | | | | | | | |
| NP swab for virus detection ¹¹ | | | | | | | | | X |
| Follow-up safety call | | | X | X ¹² | X | X | X | X | |
| eDiary activation for recording solicited ARs (7 days) ¹³ | | X | | | | | | | |

| Visit Number | | 1 | 2 | 3 | 4 | 5 | 6 | 7 | USV |
|---|------------------------|--|------------------------------|--------------------|-----|------|---------------------------------------|----------|-----------|
| Type of Visit/Contact | C | C | SC | C ¹ /SC | SC | SC | SC | SC | C |
| Month Timepoint | | | | M1 | M3 | M6 | M9 | M12 | Up to M12 |
| Study Visit | Screening ² | D1 (Baseline) | D8 | D29 | D91 | D181 | D271 | D361/EoS | USV |
| Window Allowance (Days) | -28 | N/A | ±2 | -7 to +3 | ±5 | ±14 | ±14 | ±14 | N/A |
| Review of eDiary for solicited ARs | | | X | | | | | | |
| Symptom Reporting eDiary activation ¹⁴ | | X | | | | | | | |
| Symptom Reporting eDiary for collection of symptoms of ILI ¹⁵ | | Twice weekly from Day 1 to Day 181 | | | | | Once weekly from Day 182 to Day 361 | | |
| Review of Symptom Reporting eDiary | | Review participant recorded ILI starting on Day 1 through Day 361 (Month 12)/EoS | | | | | | | |
| Telephone/electronic contacts to remind participants of ILI eDiary reporting ¹⁶ | | Once weekly from Day 1 to Day 181 | | | | | Every 2 weeks from Day 182 to Day 361 | | |
| eDiary collection of EQ-5D-5L ¹⁷ | | X | | | X | X | X | X | X |
| eDiary collection of WPAI:ILI | | | eDiary prompts ¹⁸ | | | | | | |
| Recording of unsolicited AEs | | X | X | X | | | | | |
| Recording of any SAEs, AESIs, and MAAEs, as well as AEs that led to discontinuation and relevant concomitant medications/procedures ¹⁹ | | X | X | X | X | X | X | X | X |
| Recording of concomitant medications and nonstudy vaccinations ²⁰ | | X | X | X | X | X | X | X | |
| Recording of hospitalizations and outpatient treatment related to or for the treatment of the MAAE or SAE ²⁰ | | X | X | X | X | X | X | X | X |
| Study completion | | | | | | | | X | |

Abbreviations: AE = adverse event; AESI = adverse event of special interest; AR = adverse reaction; C = clinic; COVID-19 = coronavirus disease 2019; D = day; eCRF = electronic case report form; eDiary = electronic diary; EFS = Edmonton Frail Scale; EoS = end of study; EQ-5D-5L = EuroQol 5-dimension 5-levels; EQ-VAS = EuroQol visual analogue scale; HRQoL = health-related quality of life; ILI = influenza like illness; IM = intramuscular; M = month; MAAE = medically attended adverse event; N/A = not applicable; NP = nasopharyngeal; SAE = serious adverse event; SARS-CoV-2 = severe acute respiratory syndrome coronavirus 2; SC = safety call (or contact by electronic means); USV = unscheduled visit; WPAI:ILI = Work Productivity and Activity Impairment Questionnaire: Influenza-like Illness.

Note: In accordance with FDA Guidance on Conduct of Clinical Trials of Medical Products during the COVID-19 Public Health Emergency ([FDA 2020](#)), investigators may convert clinic visits to telemedicine visits with the approval of the Sponsor.

1. Day 29 clinic visit is only required for participants in the immune response biomarker subset.
2. The Screening visit and Day 1 may be performed on the same day or a different day. Additionally, the Screening visit may be performed over multiple visits if within the 28-day screening window.
3. Verbal medical history is acceptable.
4. A full physical examination, including height and weight, will be performed at the Screening visit; symptom-directed physical examinations may be performed at other clinic visits. Interim physical examinations will be performed at the discretion of the Investigator. Any clinically significant finding identified by a healthcare professional during clinic visits should be reported as a MAAE.
5. Systolic and diastolic blood pressures, heart rate, respiratory rate, and body temperature. The preferred route of temperature assessment is oral. On the day of vaccination, vital signs will be collected once before vaccination and once 30 minutes after vaccination. Vital signs may be collected at other clinic visits in conjunction with a symptom-directed physical examination.
6. A point-of-care urine pregnancy test will be performed at the Screening visit and before the vaccine dose on Day 1, if Day 1 is not on the same day as the Screening visit. At the discretion of the Investigator, a pregnancy test either via blood or point-of-care urine can be performed at any time. The participant's follicle-stimulating hormone level may be measured at the Screening visit, as necessary, and at the discretion of the Investigator, to confirm postmenopausal status.
7. In a subset of participants, samples will be collected for future immune response biomarkers assessment. Of the people who participate in the subset, an additional blood sample collection for transcriptomics will be optional. Samples on Day 1 must be collected prior to receipt of vaccination.
8. Sample collection for future research sample including genomics is optional. Samples on Day 1 must be collected prior to receipt of vaccination.
9. All participants will be randomized to receive a single IM injection.
10. Assessment of EFS will only be performed for participants aged 65 years and older.
11. The NP swab specimen(s) for pathogens, including influenza virus and other respiratory pathogens (e.g., SARS-CoV-2) will be collected any time from Day 1 to Day 361 (Month 12)/EoS if participants have protocol-defined ILI per the ILI Case Definitions. If participants experience ILI symptoms, they will be instructed to contact the clinic and have an NP swab collected for testing within 72 hours. NP swabs should be collected prior to any antiviral therapy, if possible. NP swabs may be collected as part of a home visit in lieu of a clinic visit. In the event that NP swabs during ILI cannot be collected, any available influenza testing results performed outside of the study should be captured in the eCRF.
12. Only for those participants not in the immune response biomarker subset who otherwise would have a clinic visit this day.
13. The eDiary entries will be recorded at approximately 30 minutes after injection while at the clinic with instruction provided by the clinic staff. Study participants will continue to record in the eDiary for solicited ARs each day after they leave the clinic, preferably in the evening and at the same time each day, on the day of injection and the subsequent 6 days following injection.
14. The Symptom Reporting eDiary will be activated for collection of ILI symptoms starting at Day 1 and lasting until Day 361 (Month 12)/EoS.
15. Participants will be instructed to report via Symptom Reporting eDiary or telephone calls whether ILI symptoms have been experienced. If participants experience ILI symptoms, they will be instructed to contact the clinic and have an NP swab collected for testing within 72 hours. NP swabs should be collected prior to any antiviral therapy, if possible. NP swabs may be collected as part of a home visit in lieu of a clinic visit.
16. Telephone/electronic contacts are to remind participants of ILI eDiary reporting, not to capture AEs.
17. For participants reporting symptoms of ILI, the EQ-5D-5L responses will be collected using the eDiary on the day of the symptoms reporting (+1 day) and 5 days (+1 day) later.

18. For participants reporting symptoms of ILI, the WPAI over the previous 7 days will be collected using the eDiary at 5 days (+1 day) following the start of ILI symptoms reporting.
19. Trained study personnel or designee will call all participants to collect information relating to any MAAEs, AEs leading to study discontinuation, SAEs, AESIs, and information on concomitant medications associated with those events. All concomitant medications relevant to or for the treatment of an SAE, AESI, or MAAE will be recorded from Day 1 through Day 361 (Month 12)/EoS.
20. All concomitant medications and non-study vaccinations will be recorded through 28 days after study intervention (including receipt of any authorized or investigational COVID-19 vaccine). Additionally, certain concomitant medications will be recorded through Day 361/EoS.

